5.2 Efficacy Evaluations

5.2.1 Diagnostic Tests, Scales, Measures, etc.

To gather feedback on the proposed CST program, clinicians and parents who participated in the co-design will be asked in focus groups which aspects of the training would facilitate their participation in a family meeting and sense of collaboration, which opportunities might have been missed, and whether the training addresses the core competencies in collaboration. Based on participant experience and feedback in the co-design sessions, the training will be modified to ensure its goals are met. A more complete outline of the co-design group is described below in the Appendix 11.5.

Clinicians who participate in the intervention will be given a course evaluation to determine their perception of the usefulness and satisfaction with CST. They will be asked to rate their level of agreement with aspects of the course on a 5 point Likert-type scale, have their level of burnout assessed using the Maslach burnout score,¹⁰³ complete questions regarding changes that they have implemented regarding family meetings due to the 2020 COVID-19 pandemic, and provide basic demographics. A random sample of 8 clinicians will also complete a 15-30 acceptability interview 1 month after the completion of the CST training.

To evaluate team member perception and satisfaction with collaboration in actual family meetings, a validated tool will be used. The Baggs CSACD-N tool^{94,109} will measure team member perception and satisfaction with collaboration both pre and post-CST.

To evaluate clinician behavior in actual meetings we will revise a content-based coding scheme for observable behaviors that reflect skills learned in the training. We will start with a coding scheme previously used in the VitalTalk studies given the significant overlap in learning goals^{29,121,122}. The small number of new codes added will measure engagement by the attending physician of team members from other disciplines, and adherence to elements of best practices in family meetings (e.g., facilitating introductions of participants, setting an agenda, and summarizing what was discussed in the meeting). Coders will be trained in the coding scheme using a manual with detailed definitions of all the codes. All coders will code 2 or 3 co-design encounters together to obtain a consensus. Coders will also be trained in the Medical Interaction Process System (MIPS) coding scheme. MIPS draws upon a patient-centered approach and codes individual utterances between providers and patients, allowing for coding of both content and affective information⁸⁰. Because multiple clinicians will participate in any meeting, acknowledgement of a skill will be attributed both collectively to the clinician team and to the individual from a specific discipline. For example, it may be the case that before CST only the social worker verbally expresses empathy, but post-CST attending physicians and bedside nurses also verbally express empathy in a meeting. This would be considered a change in clinician behavior if either more verbal expressions of empathy are made overall or if more clinicians from different disciplines make the same total number of verbal expressions of empathy. To evaluate if there are differences in clinician behavior pre and post-CST, coders will be blinded to whether an audio file was made prior to or after CST, and whether it was in a simulated or actual clinical encounter by playing files in a random order.

To evaluate team function, the time each member speaks during the simulated or actual family meeting will be measured. We will compare the change in the number of minutes that clinicians from each discipline speak in pre and post-CST meetings using linear regression and controlling for the length of the meetings. We will slightly modify a team function tool, the PACT-Novice to measure team function in the team meetings¹²⁵. In addition, we will use an evaluation tool which was recently developed by Bruce et al. that can be used to assess family meetings and clinician skills used during meetings to assess individual and team function¹²⁶.

To evaluate the fidelity of the intervention implementation in the post-intervention phase, a Fidelity Checklist used for each recorded meeting will be used.

Taken together, the aforementioned measures will be used to assess the efficacy of the study intervention, including the development of the CST program, its perceived usefulness and satisfaction, its impact on communication skills and team function in simulated family meetings, and its impact on communication skills and team function in actual family meetings.

6 STATISTICAL CONSIDERATIONS

6.1 Primary Endpoint

The focus group will yield qualitative data on how to improve the CST program.

6.2 Secondary Endpoints

The following secondary endpoints will be used to assess CICU providers' perception of usefulness and satisfaction:

- Standard descriptive statistics and differences in means and medians will be determined for perception of usefulness and satisfaction with CST.

The following secondary endpoints will be used to assess CST impact on clinician behavior in simulated and actual family meetings:

- Feasibility of the study will be evaluated by tracking trial enrollment and retention rates, consent rates, rates of missing data on parent and team reported outcomes, duration of family and team meetings.
- Acceptability of the study will be evaluated with an acceptability interview and an acceptability satisfaction survey.¹²⁰
- SPIKES skills acquisition as assessed by the SCOPE tool. SPIKES is an acronym that stands for setting, perception, invitation, knowledge, emotion, and summary. It is a stepwise approach for giving bad news by preparing the setting; assessing the patient's perception; making an invitation to disclose the news; sharing the knowledge about the news; responding to the patient's emotion; and summarizing the plan²⁹.
- NURSE skills acquisition as assessed by SCOPE tool. NURSE is an acronym that stands for naming, understanding, respect, support, and exploring. It measures clinicians' use of verbal empathetic expressions by how they name emotions; express understanding; show respect or praise for a patient's behavior; articulate support for the patient; and explore the patient's emotional state²⁹.
- Change in Medical Interaction Process System (MIPS) profile. MIPS is a previously validated coding scheme with good psychometric properties that was developed for training clinicians in communication and related research⁸⁰. It has been used extensively in communication analysis^{83,123}. MIPS draws upon a patient-centered approach and codes individual utterances between providers and patients, allowing for coding of both content and affective information⁸⁰.
- Team Function. Team function will be analyzed by comparing the change in the number of minutes clinicians from each discipline speak in pre and post-CST meetings using linear regression and controlling for the length of the meetings.
- Team function will also be measured by changes in PACT-Novice scores and with the family meeting evaluation tool developed by Bruce et al.¹²⁶
- Change in kind of input offered by members of clinical team.

The following secondary endpoints will be used to assess clinician burnout and changes in communication in family meetings during COVID-19 pandemic

- The Maslach burnout scale, which uses Likert-type scales to measure aspects of burnout syndrome, including emotional exhaustion, depersonalization, and decreases in feelings of accomplishment.^{103,127}
- COVID-19 impact on communication in family meetings is a novel tool with 18 questions measuring the modality of communication with families and colleagues prior to during COVID-19 pandemic.

The following secondary endpoints will be used to assess CST impact on clinician behavior only in actual family meetings:

- *Modified Baggs CSACD-N tool*^{94,128}: The Baggs CSACD-N tool will measure team member perception and satisfaction with collaboration both pre and post-CST and will be given to all participating clinician team members. This tool will capture each discipline's experience with collaboration with other team members and satisfaction with care decisions. The difference in team member perception of collaboration will be measured using the CSACD-N pre and post-CST training. Means and standard deviations will be calculated for the tool and t-tests will determine if there are significant differences for each discipline pre and post-CST.
- Qualitative thematic analysis of family meetings that will identify if there are differences in themes prior to and after CST

The fidelity of the intervention implementation will be assessed by a Fidelity Checklist.

- The fidelity checklist will be scored by a study team member while reviewing the family meeting recording and reviewing information in Epic and parental survey responses. A summary score will be calculated for each family meeting conducted and descriptive statistics will be calculated for the post-intervention family meetings.

The following secondary endpoints will be used to assess parents' perspectives about communication challenges in the CICU when talking with the clinical team:

- In-person interviews prior to the intervention: These interviews will assess parents' experiences in communicating in the CICU with the clinical team. A constructivist grounded theory approach will guide qualitative analysis of interview transcripts.
- *Control Preferences Scale for Pediatrics (CPS-P)*¹¹³: The CPS-P will measure parent preferences for participation in treatment decision making pre-intervention and will be included in the survey given to 37 participating parent-patient dyads. Descriptive statistics will be calculated for quantitative data from this survey.
- *Hospital Anxiety and Depression Scale (HAD)*¹¹⁴: The HAD Scale will measure parental levels of depression and anxiety pre-intervention and will be included in the survey given to 37 participating parent-patient dyads. Descriptive statistics will be calculated for quantitative data from this survey.
- *Impact of Event Scale-Revised (IES-R)*¹¹⁵: The IES-R will measure parental levels of post-traumatic stress disorder pre-intervention and will be included in the survey given to 37 participating parent-patient dyads. Descriptive statistics will be calculated for quantitative data from this survey.

- *Trust in Physician Scale*¹¹⁶: The Trust in Physician Scale will measure parental levels of trust in the clinical team pre-intervention and will be included in the survey given to 37 participating parent-patient dyad. Descriptive statistics will be calculated for quantitative data from this survey.
- *Pediatric Family Satisfaction with Care in the Intensive Care Unit (PFS-ICU 24)*¹¹⁷: The PFS-ICU will measure parental satisfaction with care and medical decision-making (modified for parents/caregivers of critically ill children) pre-intervention and will be included in the survey given to 37 participating parent-patient dyads. Descriptive statistics will be calculated for quantitative data from this survey.
- *Communication Assessment Tool-Team (CAT-T)*¹¹⁸: The CAT-T, adapted to team environments, will measure parental perception of communication with the medical team pre-intervention and will be included in the survey given to 37 participating parent-patient dyads. Descriptive statistics will be calculated for quantitative data from this survey. This study will generate data that: a) is of substantial descriptive interest; b) will enable the evaluation of this population of CICU clinicians; c) will enable us to test the study's hypotheses; and d) will enable us to estimate the size and precision of the associations between the variables specified in the hypotheses.
- *MyICU*: The MyICU survey¹¹⁹, is an 11 item tool adapted by the authors of the tool to assess a surrogate's perceptions of how comfortable the surrogate feels discussing potential concerns they have with their child's medical team regarding their child's care in the ICU. Descriptive statistics will be calculated for quantitative data from this survey

The following secondary endpoints will be used to assess parents' acceptability with the family-facing intervention elements:

- *Fidelity of Parent Preparation and Acceptability*: Parents will be surveyed on their use of and acceptability of Family Meeting Preparation Worksheet,¹²⁰ and their acceptability of the Family Meeting Summary Worksheet. Items will be calculated with descriptive statistics and presented with means/medians.
- *Acceptability interviews with parents*: These interviews will assess parental acceptance of the parent-facing elements of the intervention and will be coded by 2 study team members using a grounded theory approach.

The following secondary endpoints will be used to assess co-design participant engagement in the co-design process:

- A survey comprising a 14-item section measuring participants' perceptions of the Co-design leader's effectiveness, a 10-item section measuring participants' perceptions of their own involvement and commitment to the Co-design process, and demographic information.

6.3 Statistical Methods

6.3.1 Baseline Data

Clinicians Participating in Actual Family Meetings and Intervention

Burnout scales, COVID-19 communication, and demographic characteristics will be summarized by standard descriptive summaries (e.g., means and standard deviations for continuous variables such as age and percentages for categorical variables such as gender).

Parent-patient Dyad Survey Data

Baseline and demographic characteristics will be summarized by standard descriptive summaries (e.g., means and standard deviations for continuous variables such as age and percentages for categorical variables such as gender). Descriptive statistics will be calculated for quantitative data from the survey.

Parent-patient Dyad Interview Data

Transcriptions of audio recorded interviews will be coded using Nvivo 11 by 2 coders. A consensus method will be used for discrepancies. A constructivist grounded theory approach will guide qualitative analysis of interview transcripts.

Qualitative Data from Focus Groups

Two coders will develop themes using a grounded theory approach and will code the transcripts of the focus groups. NVIVO software will be used to apply codes to the transcripts by 2 independent coders. Discrepancies will be resolved by consensus.

Focus Group Survey Data

Baseline and demographic characteristics will be summarized by standard descriptive summaries (e.g., means and standard deviations for continuous variables such as age and percentages for categorical variables such as gender). Descriptive statistics will be calculated for quantitative data from the survey.

6.3.2 Efficacy Analysis

Qualitative analysis of focus groups conducted during the co-design session will identify themes for elements of the training that may need to be modified.

To evaluate the reliability and validity of the coding scheme, audio recordings from simulated family meetings will be coded and compared to coded audio recordings from pre-intervention simulated family meetings. Inter-rater reliability will be confirmed by having a random sample of 10% of the audio files coded twice by different coders. Only codes with K statistic greater than 0.6 will be included in the final analysis. Convergent validity of the revised coding scheme will be assessed by computing the correlations between the revised VitalTalk coding scheme and the comparable content categories of the MIPS. For this, audio files will be coded using both coding systems and spearman rank correlations will be calculated between the two systems. Coefficients greater than 0.50 will indicate a good level of concurrence between the behaviors measured by the two interaction systems. To evaluate if there are differences in clinician behavior pre and post-CST, coders will be blinded to whether an audio file was made prior to or after CST, and whether it was in a simulated or actual clinical encounter by playing files in a random order.

To evaluate differences in individual skills acquired (SPIKES, NURSE, interprofessional competencies) in simulated family meetings, we will use the McNemar test to compare the proportion of subjects possessing a skill pre-CST in simulated encounters with the proportion who possessed the skill after CST. Each skill will be analyzed separately. The comparison will be made for each behavior assessed and each clinician discipline that demonstrates the behavior. We will also estimate the probability that a participant who did not demonstrate a skill in the pre-CST would demonstrate that skill in the post-CST as a simple ratio. We will estimate 95% confidence intervals using standard techniques. We will also use paired t-tests to examine if there is a difference in skill acquisition (using the continuous version of each of the skill outcomes) between the pre- and post-CST intervention and Wilcoxon signed rank tests.

Team function will be analyzed for simulated family meetings by comparing the change in the number of minutes that clinicians from each discipline speak in pre and post-CST meetings using linear regression and controlling for the length of the meetings.

To assess the impact of the CST program in actual family meetings, audio recordings from actual family meetings will be coded and compared to coded audio recordings from pre-intervention actual family meetings. Since there are generally at least 2 clinicians in each team encounter, we will examine the individual skill acquisition within each part of the team encounter. Within each discipline, there are several clinicians involved in multiple team meetings. We will use fixed-effects regression with a clinician identifier variable as a covariate so that we can examine the effect of CST intervention on skill acquisition, adjusting for the effects of individual clinicians.

Team function will be analyzed in the same way as in simulated meetings by comparing the change in the number of minutes that clinicians from each discipline speak in pre and post-CST meetings using linear regression and controlling for the length of the meetings.

The difference in team member perception and satisfaction with collaboration will be measured after their participation in clinical encounters both pre and post-CST by administering the modified Baggs CSACD-N tool to all clinician team members who participate in an actual encounter. This tool will capture each discipline's experience with collaboration with other team members and satisfaction with care decisions. Means and standard deviations will be calculated for the tool and t-tests will determine if there are significant differences for each discipline pre and post-CST.

Hypotheses will be tested using logistic regression modeling with significance of the two-tailed hypothesis tests set at alpha equal to 0.05.

Clinician perception of the usefulness of CST and satisfaction with the training will be identified by descriptive statistics and differences in the mean and median scores will be calculated to determine retention in perceptions of usefulness one month after the training.

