After the consent process, clinicians will go through the interprofessional CST. The CST will occur over the course of 10 hours and will include short didactic sessions around giving bad news, eliciting parental goals, the core competencies of interprofessional collaborative practice⁸⁸, and adaptation for the CICU of the common components of a family meeting as represented in the CHOP Family Meeting Resources (http://intranet.chop.edu/sites/social_work/family-meeting-resources.html). Skills practice groups will include no more than 6 learners at a time. Didactic sessions may be in person or may be performed independently online as needed. Whether in-person or online, sessions may be audio or video recorded. There will be an online survey immediately after the CST to evaluate the clinicians' perception of effectiveness of the course. One month after the completion of the CST, a random sample of 8 participants will take part in a 15-30 minute acceptability interview regarding the CST.

Following the CST, a set of at least 23 actual family meeting encounters with trained clinicians will be audio recorded and coded.

A measure of team function will be assessed pre and post-CST by comparing the amount of time different members of the clinical team speak, and the kind of input offered by members of different disciplines within the team for simulated and actual family meetings. Team member perception and satisfaction with collaboration will be measured after their participation in clinical encounters both pre and post-CST by administering the modified Baggs CSACD-N tool to all clinician team members who participate in an actual encounter. This tool will capture each discipline's experience with collaboration with other team members and satisfaction with care decisions. Finally, fidelity of clinician behavior to the intended intervention in post-intervention family meetings will be determined by a fidelity checklist.

Actual meetings will each last 30-120 minutes. Clinicians participating in the intervention will be enrolled for the entirety of the study, lasting up to four years. They will have at least 21 points of contact with the research team, but some clinicians may participate more frequently due to the unknown composition of the observed actual family meetings.

Clinicians Not Participating in Intervention

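### The SCOPE–MIPS concurrence rule (Spearman above 0.50) takes no account of meeting length, which can inflate the coefficient where the scores are counts

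*Protocol*

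**What the plan says.** Protocol 6.3.2 assesses convergent validity by correlating "the revised VitalTalk coding scheme and the comparable content categories of the MIPS". The procedure is: "For this, audio files will be coded using both coding systems and spearman rank correlations will be calculated between the two systems". The reading rule follows: "Coefficients greater than 0.50 will indicate a good level of concurrence between the behaviors measured by the two interaction systems". The section does not say whether counts, graded scores or presence/absence are correlated. It mentions no rate, partial correlation or other control for length.

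On the scores, Protocol 5.2.1 says that MIPS "codes individual utterances between providers and patients, allowing for coding of both content and affective information". SCOPE is described there as a content-based scheme for observable behaviours. Its worked example compares numbers of empathic expressions before and after training. Section 6.3.2 refers both to the proportion possessing a skill and to a continuous version of each skill, whose scale is not defined.

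On the recordings, the paragraph opens: "To evaluate the reliability and validity of the coding scheme, audio recordings from simulated family meetings will be coded". No duration is given for simulated meetings. The clinician schedule of evaluations in 5.1.1 lists SCOPE and MIPS only for actual meetings before and after CST. For those, 3.1 states: "Actual meetings will each last 30-120 minutes". Section 3.3.1 also gives 30–90 minutes (non-participating clinicians) and 30–60 minutes (post-intervention dyads).

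Length is controlled elsewhere: the speaking-time analyses in Protocol 5.2.1, 6.2, 6.3.2 and 6.4 and in the SAP all adjust for it. The SAP does not mention MIPS or this correlation.

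**The concern.** A correlation across recordings of unequal length mixes two things: agreement about what was said, and the fact that long recordings contain more of everything. Only the first is convergent validity. Matching the categories does not remove the second, because length inflates any pair of counts that grow with time.

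The scheme is modified for this study, and this is the only check stated in the plan that it agrees with an established system. If part of the coefficient comes from length, a value just above 0.50 could be reported as good concurrence when the agreement on content is weaker than that.

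**Working it through.** **The plan's figure.** The 0.50 threshold is stated without derivation, so there is nothing to reproduce. The check is what coefficient arises when two codes have no relation except shared meeting length.

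**Inputs from the documents.** Length ranges of 30–120, 30–90 and 30–60 minutes (Protocol 3.1 and 3.3.1); at least 20 encounters per phase (6.4); an estimated 28 post-CST meetings (3.1.5).

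**Assumptions.** Length uniform over the range; counts Poisson given length and rate; mean count *m* per meeting, equal for the two codes; rates varying between meetings with a given CV, independently for the two codes.

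**Analytic check (Pearson scale).** Let *C* be the squared CV of length and *f* the squared CV of the rate. For each code the variance is m + m²(C + f + fC), and the covariance between codes is m²C. Hence

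ρ = C / [C + 1/m + f(1 + C)].

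So ρ exceeds 0.50 only if C > 1/m + f(1 + C). With f = 0 this needs m > 1/C. With very large m it needs rate CV < √[C/(1 + C)].

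| Range (min) | C | m needed if f = 0 | Rate CV limit if m is large |
|---|---|---|---|
| 30–120 | (90²/12)/75² = 0.12 | 8.3 | √(0.12/1.12) = 0.33 |
| 30–90 | (60²/12)/60² = 0.083 | 12 | √(0.083/1.083) = 0.28 |
| 30–60 | (30²/12)/45² = 0.037 | 27 | √(0.037/1.037) = 0.19 |

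The two limits trade off. At m = 10 and CV 0.3 over 30–120 minutes, ρ = 0.12/(0.12 + 0.10 + 0.09 × 1.12) = 0.12/0.321 = 0.37, which does not pass.

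**Simulated Spearman, unrelated codes, 30–120 minutes.**

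| Rate CV | Result |
|---|---|
| 0 | 0.20, 0.39, 0.57, 0.73, 0.87 at m = 2, 5, 10, 20, 50 |
| 0.2 | 0.49 to 0.70 at m = 10 to 50 |
| 0.3 | 0.49 to 0.57 at m = 20 to 50 |
| 0.33 | 0.29, 0.38, 0.46, 0.51 at m = 5, 10, 20, 50 |
| 0.5 | 0.28 to 0.37 at m = 10 to 50 |

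**Chance that a sample coefficient exceeds 0.50 (m = 5, 10, 20, 50; 30–120 minutes).**

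| Rate CV | n = 20 | n = 28 |
|---|---|---|
| 0 | 0.29, 0.66, 0.94, 1.00 | 0.26, 0.68, 0.97, 1.00 |
| 0.33 | 0.16, 0.26, 0.39, 0.54 | 0.11, 0.22, 0.38, 0.53 |
| 0.5 | 0.08, 0.12, 0.16, 0.19 | 0.05, 0.08, 0.12, 0.15 |

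**Narrower ranges.** Over 30–90 minutes with no rate variation, Spearman is 0.47 at m = 10 and 0.65 at m = 20; at CV 0.33 it is at most 0.44. Over 30–60 minutes with no rate variation it is 0.44 at m = 20 and 0.67 at m = 50; at CV 0.2 or more it is at most 0.47.

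**Presence/absence scoring over 30–120 minutes.** 0.05 to 0.09.

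**Two possible corrections, 30–120 minutes, unrelated codes.**

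| Score | Codes that scale with length | Codes that do not (m = 10 to 20, rate CV 0 to 0.2) |
|---|---|---|
| Raw | inflated, as above | 0.00 |
| Per minute | about 0.00 | 0.49 to 0.73 |
| Partial Spearman given length | about 0.00 to 0.02 | about 0.00 to 0.02 |

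Dividing both scores by the same length creates a correlation between codes that do not grow with length. The partial coefficient, (r_ab − r_aL·r_bL)/√[(1 − r_aL²)(1 − r_bL²)] computed on ranks, is near zero in both cases.

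**The case against.** The strongest reply is that the documents do not establish the conditions under which length matters most, and much of this stands.

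- **Scoring.** Only MIPS is said to code utterances. SCOPE includes once-per-meeting items such as introductions and agenda-setting, and the SAP plans proficiency cutoffs. If presence/absence is correlated, length is irrelevant. Against this, the empathy example in 5.2.1 is a count, and the score to be correlated is never defined.
- **Recordings.** The 30–120 minute range belongs to actual meetings, while the validity paragraph names simulated ones of unstated length. A reader might infer a fourfold spread in the validation files. The documents do not support that as fact, because 6.3.2 and the schedule in 5.1.1 point to different recordings.
- **Size.** Length alone does not reach 0.50 on average for rare codes or at a rate CV of 0.5.

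Two further readings are tempting and do not hold. One is that every SCOPE result depends on this rule. The only stated condition for a code to enter the final analysis is kappa above 0.6; the 0.50 figure is a label for interpretation. The other is that a shared coder also inflates the coefficient. Section 5.2.1 does say "Coders will also be trained in the Medical Interaction Process System (MIPS) coding scheme", but no document says who codes which file in which system, and the effect cannot be sized.

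The reply leaves the omission itself untouched: a threshold is applied to a coefficient that can contain a length component, in a plan that adjusts for length elsewhere.

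**Conclusion.** The concern holds in a limited form. Where the correlated scores are counts, shared length raises the SCOPE–MIPS coefficient. Over 30–120 minutes, unrelated codes can reach or exceed 0.50 if they are frequent (about 10 or more per meeting) and their rates are stable (CV about 0.3 or less), with the less frequent codes needing the steadier rates. Outside those conditions length still contributes roughly 0.15 to 0.35, so modest real agreement could be lifted over the line. These sizes rest on assumed counts, rate variation and a uniform length distribution.

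A reader might infer that the rule would generally certify a scheme with no agreement on content. That goes beyond the documents, for the reasons given under the objection. This is a modest, secondary point that is worth correcting because the better method costs almost nothing.

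**What to change.** In Protocol 6.3.2:

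1. State which score is correlated for each code (count, graded score or presence/absence) and that the unit is the recording.
2. Compute partial Spearman correlations given meeting length and apply the 0.50 threshold to those. The unadjusted coefficients can be reported beside them.
3. Do not replace this with per-minute rates for all codes, because that induces correlation for items that do not scale with length, such as introductions and agenda-setting.
4. Reconcile whether the validation files are simulated meetings (6.3.2) or actual meetings (schedule in 5.1.1).

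The cost is a sentence or two. Meeting duration is already tracked as a feasibility measure (6.2), so no extra coding is needed if the files are actual meetings; if they are simulated, their length can be read from the recordings. Reported coefficients will be lower for codes whose counts grow with length.
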